**Approval Date: 24/11/2017**

## Study protocol

A total of 265 osseointegrated implants in 75 patients were evaluated in detail for the application of second-stage surgical procedures. Conventional methods were preferred for the second-stage implant surgeries of 164 osseointegrated implants in 35 patients and they were excluded from the study because of the lack of adequate keratinized gingiva in the implant site or the fact that localization of the implant is not known due to the thickness of the gingiva. Patients who needed tissue transposition techniques (Roll flap, Palacci technique, etc.) were also not included in the study. Periapical radiographs of the implants were obtained for all patients. Implants which showed signs of probable bone growth on the closure screw were not included in the study for standardization between groups.

40 patients were found to be eligible for the second-stage surgical operation with dental lasers. The study group consisted of healthy individuals aged 18-70 years. These patients had no risk for second-stage surgery. The patients were divided into two groups by randomization procedure (<http://graphpad.com/quickcalcs/randomize1.cfm>). The systemic illness, smoking status and toothbrushing habits of all patients included in the study were recorded.

The second-stage implant surgeries of the patients in the first group ( $n = 20$ ) were performed with 940 nm Ga-Al-As diode laser (Ezlase™, BIOLASE Technology Inc, USA) and the surgeries of the second group ( $n = 20$ ) were performed with 2780 nm Er,Cr:YSGG laser (Waterlase iPlus®, BIOLASE Technology, Inc, USA).

The second-stage implant surgery of both groups began without the use of local anesthesia (LA). Patients were informed that they will be treated with topical LA (Vemcaine Pump Spray 10% 50 ml; Vem, Ankara, Turkey) if they had any pain during treatment.

In the first group, the procedures were performed with a 940 nm wavelength diode laser (Ezlase 940; Biolase Technology, Inc., Irvine, CA) according to the guidelines recommended by the manufacturer. (surgical E4 300  $\mu$ m tip, 2.5 W power, average power: 1.25 W, pulse length CP2: 1.00 ms, pulse interval: 1.00 ms, duty cycle 50%, continuous wave).

In the second group, the procedure was performed in line with the recommended "implant recovery" setting of the Er,Cr:YSGG laser with a wavelength of 2780 nm (MZ5-6mm tip, 2.00 power, 100 Hz, H mode, 10% water and 10% air). The patients were instructed to use a mouthwash containing 0.2% chlorhexidine gluconate (Klorhex Gargara, 200 mL; Drogasan İlaç, Ankara, Turkey) three times a day.

To uncover the implant, laser-assisted incisions were expanded in a circular fashion, starting from the most likely position of the implant's closure screw in both groups.

Patients were recommended to use paracetamol (Parol 500 mg tablets, Atabay Ilac San, Istanbul) as a pain reliever in the postoperative period, only when needed. VAS (Visual Analogue Scale) values (0-10), intraoperative bleeding grades (intraoperative bleeding: 1: minimal, 1, 2, 2: normal, 3: excessive hemorrhage), the number of pain relievers used in the postoperative period and the duration of operation (min) were recorded. The total operation time was divided by the number of implants, and the operation time per implant was determined and recorded. Complications observed in the wound area during the control visits were scored and noted (soft tissue inflammation: 1, edema: 2, gingival bleeding: 3).

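### No masking of patients or outcome graders is described, although four of the five recorded outcomes depend on judgement or behaviour

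*Combined protocol and SAP*

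**What the plan says.** All the relevant text is in the combined protocol and SAP, under Study protocol and Statistical methods.

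- **Allocation.** "40 patients were found to be eligible for the second-stage surgical operation with dental lasers", and "The patients were divided into two groups by randomization procedure" using an online tool, 20 to each laser.
- **Devices.** "In the first group, the procedures were performed with a 940 nm wavelength diode laser". The second group is treated with an Er,Cr:YSGG laser at the settings "MZ5-6mm tip, 2.00 power, 100 Hz, H mode, 10% water and 10% air". No water or air setting is listed for the diode laser. Both groups start without local anaesthetic.
- **Patient information.** The sentence beginning "Patients were informed that they will be treated with topical LA" goes on to make this conditional on pain during treatment. It does not mention the laser.
- **Outcomes.** The list opens with "VAS (Visual Analogue Scale) values (0-10), intraoperative bleeding grades" and continues with the number of pain relievers, which patients take as needed, and operation time in total and per implant. For the wound, "Complications observed in the wound area during the control visits were scored and noted". Nobody is named as grader of bleeding or complications.
- **Analysis.** VAS is modelled with a negative binomial generalized linear mixed model. Laser group, time, sex and brushing are fixed effects; operation duration and age are covariates.

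Neither section mentions blinding, masking, concealment of the device or an independent assessor.

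**The concern.** A patient who knows which laser was used, and has a view about it, may rate pain or take tablets in line with that view. A clinician grading on a coarse bleeding or complication code can do the same without intending to. An average difference between groups that arises in this way enters the laser comparison and cannot be told apart from a true laser effect.

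The design makes partial protection possible. Both arms are active lasers, both begin without local anaesthetic, and both uncover the implant by widening circular incisions. A patient therefore need not be told which device is in use, and a control-visit scorer who did not operate need not be shown it. The plan takes neither step.

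**Working it through.** **1. Who determines each outcome, and what masking is described**

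| Outcome | Determined by | Masking described |
|---|---|---|
| VAS pain, 0-10 | Patient (self-rating is inherent to the scale) | None |
| Number of pain relievers | Patient, as needed | None |
| Intraoperative bleeding grade | Grader not named; graded during surgery, with the laser in view | None |
| Complication score | Grader not named; scored at control visits | None |
| Operation time | Operator's pace; no start or stop rule given | None |

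The first four depend on judgement or behaviour. Time is recorded in minutes, so it is less exposed. It is not immune, because the operator knows the laser and sets the pace. Duration is also a covariate in the VAS model.

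**2. Whether another part of the plan removes the problem**

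Randomisation balances patients at allocation, whereas knowledge of the device arises afterwards. The model adjusts for time, sex, brushing, operation duration and age. None of these separates an expectation effect from the laser effect, because both run along the same group contrast.

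**3. Illustration of size**

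The documents give no alpha, power, SD, effect size or sample-size calculation, so there is no stated figure to reproduce. The only documented input is n = 20 per group. The SD and the size of the shift are assumptions.

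Standard error of a difference in mean VAS = SD × sqrt(1/20 + 1/20) = SD × 0.316.

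- At an assumed SD of 1.7: 1.7 × 0.316 = 0.54. Shifts of 0.3 and 1.0 points are then 0.3/0.54 = 0.6 and 1.0/0.54 = 1.9 standard errors.
- Across assumed SDs of 1 to 2.5, the standard error runs from 1 × 0.316 = 0.32 to 2.5 × 0.316 = 0.79.

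Chance that a two-sided 5% two-sample t test (38 degrees of freedom) rejects when the lasers do not differ, from the noncentral t with noncentrality (shift/SD) × sqrt(20/2):

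| Assumed shift | Rejection rate |
|---|---|
| 0.1 SD | 6% |
| 0.2 SD | 10% |
| 0.3 SD | 15% |
| 0.5 SD | 34% |

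The same calculation in VAS points:

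| Assumed SD | 0.5-point shift | 1-point shift |
|---|---|---|
| 1 | 34% | 87% |
| 1.5 | 18% | 54% |
| 2 | 12% | 34% |
| 2.5 | 10% | 23% |

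For the bleeding grade, each patient regraded in one group moves a category's share by 1/20 = 5 percentage points; three patients move it by 3/20 = 15 points.

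**4. What the illustration cannot show**

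The planned VAS analysis is a negative binomial mixed model, chosen because of excess zeros. If the usual log link is used, a shift in points does not simply add to the estimated laser effect. Where many scores are zero there is little room for a downward shift. The rates above apply to a comparison of means, not to the planned test.

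**The case against.** The strongest objections, and what stands of each:

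- **Silence is not a statement of open-label conduct.** A reader might infer that patients and graders knew the laser. The documents do not say so, and consent material is not in the text available. This stands: the supportable statement is that no masking is described. It does not dispose of the point, because allocation, procedure, patient instructions and outcome recording are all set out without any such step.
- **The sentence on topical anaesthetic proves nothing about the laser.** Correct. It shows only that patient information was specified on one matter and not on this one. The evidence lies in the device descriptions and the outcome list.
- **No direction of bias is documented.** A reader might infer a consistent push towards one laser. The documents state no hypothesis, no favoured device and no expected pain difference, and both arms are active lasers from one manufacturer. If patients' expectations differ, much of the effect could be noise. This stands: the bias is possible and its direction unknown.
- **The numbers are assumed and on the wrong scale.** This also stands. The arithmetic is right, but it shows sensitivity at 20 per group and does not estimate this trial's bias.
- **Masking would be incomplete.** The operator cannot be masked, and a patient may notice the water and air. If the operator also scores the control visits, omitting the laser from the form achieves little. These points limit the benefit but do not remove it for patient-rated pain and tablet use, where not naming the device still helps.

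**Conclusion.** The concern holds in a limited form. The plan describes no masking of patients or graders, four of the five outcomes depend on judgement or behaviour, and neither randomisation nor the planned model removes a bias that arises from knowing the device. It would be tempting to exempt operation time, but the documents do not support that: the operator knows the laser and no timing rule is given.

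Neither size nor direction can be determined from the documents. Under an assumed shift of 0.1 to 0.5 SD and a simple comparison of means with 20 per group, the nominal 5% error rate would rise to between about 6% and 34%. The conclusion does not rest on that range. It rests on the absence of any described safeguard and on a partial safeguard being cheap. If masking was in fact carried out, stating it would settle the point to that extent.

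**What to change.** - Tell patients only that they will receive one of two dental lasers. Do not name the device until their last VAS and tablet entry.
- Leave the laser off the control-visit form, so that complications are scored without it wherever the scorer was not the operator. State who scores.
- Report the intraoperative bleeding grade and operation time as unmasked.
- The text is in the past tense. If treatment is already complete, state who was and was not masked, and qualify these outcomes accordingly.

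**Cost.** Revised patient-information wording and one field removed from a form, with no extra staff or visits. Patients learn their allocation only at the end. Masking remains incomplete because the devices can be told apart in use: the settings "H mode, 10% water and 10% air" belong to the Er,Cr:YSGG laser, and none are listed for the diode.

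### Do a stray emission-mode label and an unassigned mouthwash sentence mean that the two laser arms differ in more than the laser?

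*Combined protocol and SAP*

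**What the plan says.** Under Study protocol, the diode arm's setting is given in one parenthesis: "2.5 W power, average power: 1.25 W, pulse length CP2: 1.00 ms, pulse interval: 1.00 ms, duty cycle 50%, continuous wave". It lists a set power and a mean power, then the pulse timing, and ends with a duty cycle and an emission mode.

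The Er,Cr:YSGG setting follows in a paragraph that opens by naming the second group. The next sentence of that paragraph reads "The patients were instructed to use a mouthwash containing 0.2% chlorhexidine gluconate", three times a day, and names no group. The first-group paragraph has no such instruction, and mouthwash is not mentioned again.

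Two other shared steps are assigned explicitly to both arms: starting surgery without local anaesthesia, and the circular incision ("closure screw in both groups").

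Under Statistical methods, the VAS model has laser group, time, sex and brushing as factors, and operation duration and age as covariates. Mouthwash is not among them.

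**The concern.** There are two separate worries.

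- **Diode setting.** Continuous emission has no gap between pulses, so its mean power equals its set power. A 50% duty cycle halves it. The line states both, so someone repeating the diode arm could ask whether the mean power was 1.25 W or 2.5 W. The setting defines one of the two randomised interventions, so this is not a trivial place for a contradiction.
- **Mouthwash.** Read by its position alone, the sentence gives an antiseptic rinse to the second group only. The complications scored at control visits are soft tissue inflammation, edema and gingival bleeding, which a rinse could plausibly affect. Randomisation does not protect against a co-intervention assigned by arm. If 20 of the 40 patients rinsed and they were exactly the Er,Cr:YSGG arm, a difference in complications, and possibly in pain or analgesic count, could not be credited to the laser.

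**Working it through.** **Diode setting.** All inputs come from the diode parenthesis in Study protocol: set power 2.5 W, mean power 1.25 W, pulse length 1.00 ms, pulse interval 1.00 ms, duty cycle 50%.

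1. The plan's own figures, taking the interval as the time off:
   - Duty cycle = on / (on + off) = 1.00 / (1.00 + 1.00) = 50%, as stated.
   - Mean power = set power × duty cycle = 2.5 W × 0.50 = 1.25 W, as stated.
2. Continuous emission: duty cycle 100%, so mean power = 2.5 W × 1.00 = 2.5 W. This is 2.5 / 1.25 = 2 times the stated mean. There would be no pulse length or interval to report.
3. Interval read instead as start-to-start period: 1.00 / 1.00 = 100%, mean 2.5 W. This contradicts both the stated 50% and "average power: 1.25 W", so it does not rescue the label.

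The five numbers form one coherent set, and the label is the only item outside it. To reach 2.5 W a reader must set aside the mean power and the duty cycle that the text gives outright.

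**Mouthwash.** No arithmetic settles this, so the sentences are set side by side.

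- Expressly for both arms: the start without local anaesthesia, and the incision.
- No group named, yet plainly for everyone: the randomisation sentence, whose subject is the same as that of the mouthwash sentence and means all 40 patients; the notice about topical anaesthetic, which follows a sentence covering both arms; the paracetamol advice; and the recording of VAS, bleeding grade, analgesic count, operation time and complications.
- No group named, scope unclear: "The patients were instructed to use a mouthwash containing 0.2% chlorhexidine gluconate".

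The document therefore does not reserve unqualified wording for a single arm. The subject also changes within the paragraph, from the laser procedure to the patients. What remains for the one-arm reading is the sentence's position.

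**What would follow if the one-arm reading were true.** A mouthwash indicator would equal the laser-group indicator for all 40 patients, 20 with 1 and 20 with 0. The two effects could not be estimated separately, and adding mouthwash to the model would not help. The outcomes exposed would be the postoperative ones. The timing of the rinse is not stated. If it was used after surgery, intraoperative bleeding and operation time could not be affected.

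**The case for a change.** The strongest case for acting is that both points are real on the page and cheap to settle. The diode line contradicts itself under either reading of the interval. Continuous wave might name the class of laser, or mean interrupted continuous emission, but the text does not say so. On the mouthwash, the sentences that use unqualified wording for everyone do not sit in paragraphs limited to one group, whereas the mouthwash sentence does. A rinse confined to one arm would be a confounder that no analysis could remove.

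Part of this stands. The label and the figures must be reconciled, and the mouthwash sentence should name its group or groups. Only the sponsor can do either.

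The step from there to a flaw in the trial does not stand. The diode contradiction lies inside one arm's laser description, so it cannot show that the arms differ in anything besides the laser. That inference rests wholly on the mouthwash sentence, whose scope is open. The factor of 2 measures the distance between a label and the figures beside it, not a known departure in treatment. The documents also do not say how mean power or rinsing affects pain, bleeding or healing, so no size of bias can be given.

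**Conclusion.** No change to the plan follows. The diode point is a clerical inconsistency: one label disagrees with five figures that agree with one another (50% and 1.25 W reproduced exactly), and tidying it alters no analysis or result. The text must be reconciled. This check does not say which description matches the setting used. The documents give no reason to think that the mean power was other than the stated 1.25 W, but they cannot prove what was delivered.

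The mouthwash point is a missing detail. A shared postoperative instruction is a natural reading, given how the document uses unqualified wording elsewhere, and a reader can settle it by asking the sponsor. Naming the group or groups records what was done; it offers no better method.

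The conclusion rests on one assumption, that the rinse was not confined to one arm. If it was confined, the figure of 20 of 40 patients becomes real. The postoperative comparisons (wound complications, possibly pain and analgesic count) would then have to be described as laser plus mouthwash against laser alone. The text does not establish that case.

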### **Statistical methods**

Characteristics of the study participants for the continuous variables were analyzed by t test after Shapiro Wilk normality test for comparisons between the diode and Er,Cr:YSGG laser groups. For the categorical variables were analyzed by Pearson chi squared test and likelihood ratio chi squared test, as appropriate, for comparisons between the diode and Er,Cr:YSGG laser groups.

Generalized linear mixed model (GLMM) was used for analysis of VAS outcomes. Fixed effects factors in GLMM were used laser groups, time (days), sex, and brush and as covariates operation durations and age. The results of GLMM was obtained according to residual subject specific pseudo likelihood method with ar(1) covariance structure and negative binomial distribution because of data possess an excessive of zeros. Holm-Tukey multiple comparison adjustment were used for the p-values and obtained confidence limits for the differences of LS-means. The analyses were performed using SAS version 9.4 statistical software (SAS Institute Inc, Cary, North Carolina, USA).

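### The only VAS model adjusts for operation duration, which arises after randomisation, so its laser contrast may not be the total laser effect

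*Combined protocol and SAP*

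**What the plan says.** The Study protocol section reports that "40 patients were found to be eligible for the second-stage surgical operation with dental lasers" and that "The patients were divided into two groups by randomization procedure", 20 to the diode laser and 20 to the Er,Cr:YSGG laser. Duration comes from the operation itself: "the number of pain relievers used in the postoperative period and the duration of operation (min) were recorded". A second version is derived from it: "The total operation time was divided by the number of implants, and the operation time per implant was determined and recorded".

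The Statistical methods section analyses VAS with one negative binomial GLMM with AR(1) covariance. Its terms are given as: "Fixed effects factors in GLMM were used laser groups, time (days), sex, and brush and as covariates operation durations and age". For inference it "obtained confidence limits for the differences of LS-means". It describes no VAS model without duration and no sensitivity analysis, and it does not say that a contrast at equal duration is the one intended.

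**The concern.** Randomisation protects the comparison of the two lasers as allocated. A variable measured during the operation, with the allocated laser in use, can itself be changed by that laser. Holding it fixed removes any part of the laser effect that acts through duration. It also opens a second route: anything left out of the model that affects both duration and pain then distorts the laser contrast, even if duration has no effect on pain. Pain sensitivity could be such a factor, because surgery began without local anaesthesia and topical anaesthetic was offered if pain occurred. That is an inference; the documents do not report it.

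Because only the adjusted model is described, a reader could not tell whether a reported pain difference, or its absence, depends on this covariate. A contrast at equal duration is a legitimate but different question.

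The covariate is also undefined. Total time depends on the number of implants, which is not in the model; time per implant does not carry it in the same way.

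**Working it through.** The documents give no sample size calculation, effect size, SD, duration result or duration-VAS relation, so there is no stated figure to reproduce. The arm sizes (20 and 20) and the implant counts come from the Study protocol section. Everything else below is assumed, to show the range.

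**1. Linear illustration (mean VAS per patient).** Let g be the laser (0 or 1), d the duration shift caused by the laser in within-arm SDs, and r the within-arm correlation of duration with VAS.

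- Duration: D = d·g + U
- VAS: y = T·g + r·U + √(1 − r²)·e, where T is the total laser effect in SDs
- Substituting U = D − d·g gives y = (T − r·d)·g + r·D + √(1 − r²)·e

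The duration-adjusted contrast is therefore T − r·d, a bias of −r·d, which is zero if either d or r is zero. With d = 0.5, r = 0.1 gives 0.05 SD and r = 0.5 gives 0.25 SD in absolute size.

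Type I error of the adjusted test with T = 0, 20 per arm, two-sided 5%, 40,000 simulated trials per cell:

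| d | r = 0 | r = 0.1 | r = 0.3 | r = 0.5 |
|---|---|---|---|---|
| 0 | 5.0% | 5.1% | 4.8% | 4.9% |
| 0.2 | 5.1% | 5.0% | 5.6% | 6.5% |
| 0.5 | 5.0% | 5.3% | 7.5% | 13.8% |

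Without duration in the model the rate is 4.8% to 5.2%.

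**2. Power with a true effect of 0.9 SD** (79% without duration), |d| = 0.5:

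| | r = 0.1 | r = 0.3 | r = 0.5 |
|---|---|---|---|
| More painful laser slower: estimate (SD) | 0.85 | 0.75 | 0.65 |
| Power | 71.0% | 64.1% | 59.9% |
| More painful laser faster: estimate (SD) | 0.95 | 1.05 | 1.15 |
| Power | 80.2% | 89.8% | 97.3% |

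Not all of the loss in the slower case is bias. At d = 0.5 and r = 0, where bias is zero, power is 76%, so about 3 points come from collinearity alone.

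**3. Log-link form, closer to the planned model** (the link is not stated; log is assumed). With a the duration shift in SDs and b the log rate ratio of VAS per SD of duration, log RR(adjusted) = log RR(total) − a·b. For a total RR of 0.70:

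- a = 0.25, b = 0.1: 0.70·exp(−0.025) = 0.683
- a = 0.5, b = 0.2: 0.70·exp(−0.10) = 0.633
- a = 1, b = 0.4: 0.70·exp(−0.40) = 0.469

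Large-sample negative binomial fits (200,000 observations) agree. RR without and then with duration:

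- laser does not change duration: 0.697 and 0.697
- duration unrelated to VAS: 0.705 and 0.706
- both conditions met (a = 1, b = 0.3), total RR 0.70: 0.700 and 0.519
- effect wholly through duration, total RR 1.5: 1.494 and 0.998
- no laser effect on VAS, unmeasured common cause of duration and VAS: 1.008 and 0.822

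**4. Repeated measures at 20 per arm.** This check assumed 4 visits, about 61% zeros and AR(1) latent effects, with a negative binomial GEE standing in for the SAS pseudo-likelihood GLMM and 2,000 runs per cell. With d = 0.5 and no laser effect, the adjusted RR is 0.87 (type I error 6.9%) at a within-arm correlation of 0.28, and 0.79 (11.6%) at 0.44. Without duration, the RR is 1.01 (4.8%) and 1.00 (6.1%).

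**5. Which duration.** "A total of 265 osseointegrated implants in 75 patients were evaluated in detail", and "Conventional methods were preferred for the second-stage implant surgeries of 164 osseointegrated implants in 35 patients". By subtraction, 265 − 164 = 101 implants in 75 − 35 = 40 patients, or 101/40 = 2.525 per patient if none were dropped later. Assume pain is related only to the number of implants (correlation 0.3 to 0.5), with no laser effect on VAS, and a coefficient of variation of time per implant of 0.2 to 0.4. Total time then correlates 0.91 to 0.74 with the number of implants. Using total time as covariate:

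- laser shifts time per implant by 0.5 SD: type I error 5.2% to 5.6% at correlation 0.3, and 5.9% to 6.5% at 0.5
- laser shifts it by 1 SD (0.34 to 0.54 SD of total time): bias 0.09 to 0.21 SD in absolute size, type I error 6.0% to 10.2%

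With the number of implants as covariate in the 1 SD case, bias is within 0.003 SD and type I error is 4.9% to 5.1%.

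**The case against.** The strongest reply is that harm is possible but not shown. Bias needs a duration difference caused by the laser and a within-arm relation of duration to VAS, and the documents establish neither. A chance imbalance in duration that comes from a baseline factor would not make the adjustment wrong. Modest inputs also give modest effects: at d = 0.5 and r up to 0.3 the bias is at most 0.15 SD, about half of a standard error near 0.3 SD, and the type I error is at most 7.5%. A sign change can be constructed (d = r = 0.5 turns a true 0.20 SD into 0.20 − 0.25 = −0.05 SD), but an effect that small is not detectable with 20 per arm in either model, so the example carries little weight. In the repeated-measures check, the model without duration already rejects 6.1% in the strongest cell, so the excess due to duration there is 11.6 − 6.1 = 5.5 points.

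All of that stands, and it limits what can be said about size. It does not answer the main point: the one analysis described for VAS does not target the randomised contrast unless one of two unreported quantities is zero, and no result is described that would let a reader check. Adjustment can add precision, but operative extent can be represented by the number of implants without using a variable measured after allocation.

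**Conclusion.** The concern holds in its conditional form and should be fixed. The laser contrast in the only VAS model equals the total effect of allocation only if the laser does not change duration or duration is unrelated to VAS within laser group. The actual bias and its direction are unknown. On assumed inputs it runs from nothing to about 0.25 SD, with type I error up to about 14% at a duration shift of half an SD and a within-arm correlation of 0.5; larger shifts give more. Confidence is high in the algebra and in the absence of a model without duration. It does not extend to a claim that this trial's contrast is materially wrong. The ambiguity between total and per-implant time adds to the problem, because total time brings in the number of implants.

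**What to change.** Make the main VAS GLMM laser group, time, sex, brush and age, without operation duration. Report the duration-adjusted GLMM beside it as a labelled secondary analysis, and say whether it uses total or per-implant time. The Statistical methods section is written in the past tense, so label the refit as a revised analysis.

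Optionally, if operative extent should be adjusted for, add the number of implants per patient. It is already used as the divisor for time per implant. That it was settled before allocation is a reasonable reading of the order of the text, not a stated fact, and should be confirmed. Duration can be compared between lasers as an outcome; if the t tests already cover it, report that result as such. It does not repair the VAS contrast.

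Cost: one refit (two if the number of implants is added), a few sentences and no new data. If duration predicts VAS but does not differ by laser, some precision is lost. The standard error without duration is √(2/20) ≈ 0.32 SD, against about 0.30 to 0.31 (r = 0.3) or 0.28 (r = 0.5) with it. If VAS correlates 0.5 with the number of implants, adjusting for that number gives about 0.28, against 0.29 to 0.30 with total time and 0.31 to 0.32 with neither.

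### The VAS model adjusts for operation duration, measured after randomisation, but not for smoking status, a baseline factor recorded for every patient

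*Combined protocol and SAP*

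**What the plan says.** The Study protocol section lists three patient factors collected from everyone: "The systemic illness, smoking status and toothbrushing habits of all patients included in the study were recorded". On allocation it says "The patients were divided into two groups by randomization procedure", with 20 patients in each group and no stratification factor mentioned. It also says that operation time in minutes was recorded, both as a total and per implant.

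The Statistical methods section states "Generalized linear mixed model (GLMM) was used for analysis of VAS outcomes" and then gives the terms: "Fixed effects factors in GLMM were used laser groups, time (days), sex, and brush and as covariates operation durations and age". Toothbrushing is therefore the only one of the three recorded patient factors in the model. No reason is given for including it and leaving out smoking, or for including duration. Baseline characteristics are compared between arms separately: "For the categorical variables were analyzed by Pearson chi squared test and likelihood ratio chi squared test, as appropriate".

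**The concern.** Two features of the covariate list pull in the wrong direction.

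**Operation duration is included.** It arises during the laser procedure, so it is not fixed at randomisation, and the type of laser may affect it. If one laser takes longer and longer procedures hurt more, conditioning on duration removes part of the laser's own effect: the contrast becomes one between lasers at equal duration. If an unmeasured factor, such as how hard the implant is to uncover, drives both duration and pain, conditioning on duration can also tie that factor to the laser group, which randomisation had kept separate.

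**Smoking is left out.** It is a patient characteristic already in the data set. If it relates to postoperative pain, adjusting for it would sharpen the laser contrast and remove the effect of any chance difference in smoking between two arms of 20.

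**Working it through.** **1. The plan's own figure.** 75 patients evaluated − 35 excluded = 40 = 20 + 20, as stated. The documents give no sample-size calculation, VAS standard deviation, smoking prevalence, smoking effect or duration by arm. Smoking figures below therefore rest on stated assumptions, and the effect of adjusting for duration cannot be computed.

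**2. The variables side by side.**

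| Variable | Fixed before allocation? | In VAS model? |
|---|---|---|
| Sex, age | Yes | Yes |
| Toothbrushing | Yes | Yes |
| Smoking | Yes | No |
| Systemic illness | Yes | No |
| Operation duration | No, arises in the procedure | Yes |

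**3. How often would smoking be imbalanced?** Take the smokers per arm as two independent Binomial(20, p) counts. A gap of 20 points is 4 patients, so the probability needed is P(|X₁ − X₂| ≥ 4), summed exactly. The prevalence p is assumed.

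| p | ≥10 points | ≥20 points | ≥30 points |
|---|---|---|---|
| 0.1 | 0.42 | 0.06 | 0.004 |
| 0.2 | 0.55 | 0.16 | 0.03 |
| 0.3 | 0.60 | 0.23 | 0.06 |
| 0.4 | 0.63 | 0.26 | 0.08 |
| 0.5 | 0.64 | 0.27 | 0.08 |

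With the total number of smokers fixed at 4, 8, 12, 16 or 20 of 40 (hypergeometric), the probability of 20 points or more is 0.11 to 0.34. These totals are all even, which makes the difference in counts even as well. An odd total would need a gap of 5 patients.

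**4. How far would it move the contrast?** On a linear scale at one time point, the standard error (SE) is √(1/20 + 1/20) = 0.316 SD. The shift is imbalance × smoking effect:

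- 20 points, 0.5 SD effect: 0.20 × 0.5 = 0.10 SD; 0.10/0.316 = 0.32 SE.
- 20 points, 1 SD effect: 0.20 × 1 = 0.20 SD; 0.20/0.316 = 0.63 SE.
- 10 points, 0.5 SD effect: 0.10 × 0.5 = 0.05 SD; 0.05/0.316 = 0.16 SE.

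**5. Does omission damage the test?** In 100,000 simulated trials (normal outcome, two-sample t test, p = 0.3, smoking omitted), type I error was 0.050 for a smoking effect of either 0.5 or 0.8 SD. Among trials with an imbalance of 20 points or more it was 0.063 (0.5 SD) and 0.076 (0.8 SD).

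**6. What does adding smoking cost or gain?** SE ratio = √[(1 − R²)(1 + 1/34)]. R² is the share of variance that smoking explains. The 34 is 40 patients less six coefficients (intercept, laser, sex, toothbrushing, age, smoking, counted as one each).

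- R² = 0: √(35/34) = 1.015, about 1.5% wider.
- R² = 0.10: √(0.90 × 35/34) = 0.963, about 4% narrower.
- Break-even: 1 − R² = 34/35, so R² = 1/35, about 3%.

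**7. Is the baseline chi-squared test a safeguard?** Take 8/20 against 3/20 smokers, a 25-point gap. The pooled proportion is 11/40 = 0.275, so z = 0.25/√(0.275 × 0.725 × 2/20) = 1.77 and p = 0.077. A gap of that size would pass as non-significant.

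**The case against.** The strongest case for the plan is that recording a variable does not commit anyone to adjusting for it, and that a short covariate list is sensible with 40 patients. Randomisation makes the comparison valid on average, and the standard error already allows for chance imbalance. Step 5 bears this out, and that part stands. Two stronger readings are therefore not supported:

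- A reader might infer that a clear smoking imbalance is likely. Step 3 shows that only a gap of about two patients is common. Twenty points or more has a probability of at most about 0.27 (0.34 with a fixed total), and the documents do not report the actual split.
- A reader might infer that omitting smoking biases the trial, or might pair a 25-point gap with a 1 SD effect to reach 0.25/0.316 = 0.8 SE. The documents nowhere say that smoking affects VAS, and a 25-point gap has a probability of only about 0.02-0.15 over the same prevalence range.

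Three further objections have some force. Systemic illness is also recorded and omitted; the protocol describes the patients as healthy, so it may carry little information, but the sponsor should say so. Duration may stand in for the extent of surgery. The number of implants is indeed known beforehand, but the time taken also reflects the laser, and the model does not separate the two. Last, the statistical section is in the past tense and justifies its distribution by the zeros in the data. Outcomes may already have been seen, which limits how far the main model should be rewritten.

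The baseline comparison could reveal an imbalance. It would not adjust for one, and step 7 shows that it is a poor trigger for doing so.

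**Conclusion.** The point holds as a minor weakness in the choice of covariates. The plan conditions on a variable measured after randomisation that the laser may affect, and leaves out a baseline variable that it already holds, without explaining either choice.

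The duration part rests on timing alone; its size and direction cannot be derived from the documents. The smoking part costs possible precision and leaves any chance imbalance uncorrected. A gap of 20 points or more has a probability of about 6-27% and would shift the contrast by about 0.3 to 0.6 SE. These figures assume a prevalence of 10-50% and a smoking effect of 0.5 to 1 SD. They are single-time linear approximations and carry over only roughly to the planned repeated-measures negative binomial model with AR(1) covariance.

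**What to change.** In the main VAS model, keep laser group and time and use baseline covariates only: age, sex, toothbrushing and smoking (yes/no). Drop operation duration from that model and report the duration-adjusted version as a sensitivity analysis, saying which duration (total or per implant) is used. State that covariates are not chosen from the baseline p-values, and give one sentence on why each is included and why systemic illness is not.

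If outcome data have already been seen, report the model with smoking as a labelled sensitivity analysis. The argument against duration does not depend on the results, but removing it at that stage should be declared as a change.

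No new data are needed. Exchanging duration for smoking leaves the number of terms unchanged if each is a single coefficient. Adding smoking widens the standard error by about 1.5% if it is unrelated to VAS and pays for itself once it explains about 3% of the variance. Dropping duration gives up whatever precision it provided, an amount the documents do not allow one to estimate.
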